7. POTENTIAL RISKS

Staff level:

Staff members could feel pressure to participate in the study. It will be made clear, through written materials and oral instruction, that staff participation in the project's evaluation is completely voluntary. The cost and implementation analyses and their purpose in understanding the feasibility of implementing NIATX and ECHO will be explained. Staff responses to interviews will be coded and responses will be accessible only by evaluation team members (survey and interview data will not be accessible to other clinic staff members). In addition, the Executive Sponsor for each site will be notified of the importance of staff not feeling coerced to participate in the study or complete staff surveys.

The potential risk for staff is that the information they provide could be offensive to members of management or their peers. Hence, protecting staff confidentiality is an important element of our protection plan. Researchers ([name], [name], [name]) trained in protecting consumer confidentiality will conduct interviews. Data collected in the interviews and surveys will have a code number assigned (as previously defined) attached prior to storing in the project dataset. In this way, we can ensure that

the interviewer (in the case of interviews) and the University of Wisconsin database administrator (in the case of surveys) will be the only person who can identify the interviewee's responses. Also, managers or other members of the organization will not see transcripts of interviews.

In summary, during the on-line consent, potential subjects will be informed of (1) the nature and purpose of the study, (2) the types of data that will be collected from, (3) measures taken to insure the confidentiality of data collected (4) their right to leave the study at any time, and (5) the timeline of the study. Consent will be documented by obtaining online IRB-approved consent forms containing all of the above information. Consent forms will be digitally based. Consent forms will be stored at the University Wisconsin – Madison on a secure server. The consumer can download a PDF of the consent form.

A Certificate of Confidentiality has automatically been granted by virtue of this study being funded through the National Institutes of Health. This provides an additional level of protection for participant data.

8. MEASUREMENT OF EFFECT

All scales used in this study, except for the Fidelity scales developed for this study, have good tested psychometric properties with similar populations. Listed below are the factors to be measured and measurement instruments with references to validation studies.

Descriptive Statistics - Organizational traits such as admission and rural v. urban will be obtained via Organizational Survey and database. Client traits such as age, gender, ethnicity, treatment offered and CJ status will also be obtained at three points during the study via the Organizational Survey and database. Staff traits such as gender, ethnicity, and certification or education level will be obtained via the Organizational Survey at three points.

REACH - The percent of patients initiated on MOUD and length of engagement will be obtained through monthly spreadsheet data completed by organizational staff or state databases.

Adoption – The percent of prescribers using MOUD will be collected through the Organizational survey at 3 points during the study. The organizations readiness for MOUD will be collected using the Organizational Readiness for Implementing Change (ORIC) scale and the Organizational Climate: Stress measure will be collected at two points in the study.

Effectiveness – Re-arrest rates will be obtained through state police databases on a yearly basis.

Maintenance –The organizational survey, which will be administered at three points during the study, will assess the likelihood of MOUD sustainability. The Physician Survey will be completed by physicians at 3 points during the study.

9. STUDY PARAMETERS

The 48 participating jails or community-based organizations will be assigned to one of four study arms;

- High-Dose Coaching & ECHO; community-based organizations (n=9), jails (n=3)
- Low-Dose Coaching & ECHO; community-based organizations (n=9), jails (n=3)
- High-Dose Coaching & No ECHO; community-based organizations (n=9), jails (n=3)
- Low-Dose Coaching & No ECHO; community-based organizations (n=9), jails (n=3)

We will use a matching strategy that groups four clinics together prior to randomization. One clinic from each four-clinic matched group will be randomized to each study arm. The matching criteria, using organizational characteristics traits, are:

- a) Referral Source
- b) Whether or not currently providing MOUD to CJ populations
- c) Admissions per year
- d) Urban vs Rural

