6. STUDY & TREATMENT PLAN

Study Design

The proposed study will implement a cluster randomized block design where staff are nested within sites. The community-based provider sites and jails will be grouped into homogeneous blocks and then randomly assigned into 2x2 design for each block. The forty-eights sites will be assigned to one of four study arms using a matching strategy within the blocks that groups four jail-clinic combination together prior to randomization. Each jail and CB treatment provider (or clinic) in these combinations will be treated as a site. For instance, if a jail has two post incarceration CB treatment providers (or clinics) in the trial, this will be 3 total sites (of the 48 sites). Within the matching block of 4 jail-clinic combinations, one jail-clinic combination will be randomized to an arm of the study. Twelve sites (that will consist of jails or post incarceration

CB treatment sites) will be assigned to each arm. The number of jails and post-incarceration sites per arm are expected to be balanced, with an anticipated 4 jails and 8 post-incarceration CB provider sites per arm.

Matching will be based on; a) number of clinic sites the jail will be including in the study (as part of the jail-clinic combination), population of the county where the jail is located, and whether or not the jail is currently providing MOUD to CJ population, and if so, what type of MOUD. The blocking procedure will reduce variability within treatment conditions and yield more precise estimates of treatment effects. This strategy will allow for the study team to examine the effects of High versus Low-Dose coaching and ECHO on MOUD use rates in large and small settings. In the study design, there will be a 12-month implementation period followed by 12 months to track sustainability. Data will be collected at baseline, 12 months and 24 months.

[figure not shown]
Intervention

There will be two “scaling-up practices” used in this study; NIATx Coaching and ECHO Clinical Mentoring. The study will look at combination of these two practices to create four intervention study arms;

- 1) High-Dose Coaching/ECHO,
- 2) Low-Dose Coaching/ECHO,
- 3) High-Dose Coaching/No ECHO, and
- 4) Low-Dose Coaching/No ECHO

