Collecting physician attitudes toward MOUD will occur at months 0, 12, and 24. An average of two prescribers are anticipated per site. Each survey will take 15 minutes or less to complete. Staff completing the surveys will receive consent documents when they are sent the survey link via REDCap. To increase survey completion rates for the Physician Surveys, the research team at UW will conduct follow-up phone calls and e-mails with the physicians at Week 1 of post-survey distribution to assure the survey receipt, then at Weeks 4 and 12-post survey distribution if surveys are not complete. This will result in 96 unique prescriber participants at baseline, and 9 new people per round at post-intervention (m12) and post-sustainability (m24), assuming 10% turnover at each round. This will result in a total of 114 unique prescribers and 288 surveys (@ 96/cycle).

The grand total of organizational surveys, at n=144, staff surveys at n=1,152, physician surveys at n=288. TOTAL will be N=1,584.

Administrative & Site Aggregate Data:

Administrative Jail Data will be collected from all 24 jail sites once every year for two years. We anticipate the data will include de-identified screening, assessment and/or intake data, demographic information, date entered/exited jail, sentence and length, etc.

Administrative State Criminal Justice Data will be obtained from state databases for all states that have a jail/community-based provider participating in the study. De-identified data will be provided once every year for two years for the participating jail jurisdictions (e.g. in Wisconsin it is counties). Data may include arrest dates, arrest offenses, court outcomes, sentence and length, etc.

Health and Treatment Provider Data will be provided by all 24 community-based treatment providers once every year for two years. De-identified data for jail based referrals would include number of referrals to OUD care, number of referrals to behavioral therapy or counseling, dates/type of care, MOUD units received, Medicaid payment data, etc.

Monthly Tracking Data will be provided by all 48 jails/community-based treatment providers on a monthly basis via spreadsheet provided by study team. Captured data for the jails will include MOUD treatment data, number screened for OUD, number receiving MOUD, number of

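### The protocol gives two randomisation rules and three jail/clinic splits; if jail-clinic combinations are the randomised unit, the planned models omit both that unit and its matched block

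*Combined protocol and SAP*

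**What the plan says.** **Unit.** Section 6 (Study Design) says: "Within the matching block of 4 jail-clinic combinations, one jail-clinic combination will be randomized to an arm of the study". A combination holds several of the 48 sites: "if a jail has two post incarceration CB treatment providers (or clinics) in the trial, this will be 3 total sites". Section 9 instead says: "One clinic from each four-clinic matched group will be randomized to each study arm".

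**Matching factors.** Section 6 lists the number of clinics attached to the jail, county population, and whether and which MOUD the jail provides. Section 9 lists referral source, current MOUD provision, yearly admissions and urban or rural location. Only current MOUD provision is on both lists.

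**Split of the 48 sites.** Section 6 (Study Design) describes arms "with an anticipated 4 jails and 8 post-incarceration CB provider sites per arm", and Section 10 (Sample Size & Power) gives the matching totals of 16 and 32. Section 9 lists, identically for each arm, "High-Dose Coaching & ECHO; community-based organizations (n=9), jails (n=3". Section 6 (Administrative & Site Aggregate Data) says "Administrative Jail Data will be collected from all 24 jail sites once every year for two years" and "Health and Treatment Provider Data will be provided by all 24 community-based treatment providers once every year for two years".

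**Analysis.** Section 10 (Intervention and Sustainability) specifies mixed models with random effects of programs and fixed effects of treatment condition and time, plus program covariates that it does not name. Power is based on 42 programs. Section 6 claims a benefit from matching, "The blocking procedure will reduce variability within treatment conditions and yield more precise estimates of treatment effects", but Section 10 names no block term.

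**The concern.** The two rules can produce different allocations. Under Section 6 a jail and its clinics always share an arm. Under Section 9 they could fall in different arms, with different coaching doses or ECHO in one and not the other. Two teams following this protocol could randomise differently and report different standard errors for the primary Reach comparison.

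If combinations are randomised, the programs inside one are not independent replicates of the treatment. They share a jail and a county, and the clinics' monthly tracking data count referrals from that jail (Section 6, Monthly Tracking Data). A model that treats every program as independently allocated then understates the standard error whenever programs in a combination share variance. Omitting the matched block acts the other way: it leaves block variance in the error term and makes the test conservative. The net effect on Type I error depends on both.

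**Working it through.** **1. Splits.** 4 × (4 + 8) = 16 jails and 32 clinics. 4 × (3 + 9) = 12 and 36. The data paragraphs give 24 and 24. All total 48, so the total does not settle which holds. With one combination per jail (an assumption suggested by the Section 6 example), there are K = 16, 12 or 24 randomised units, with 3, 4 or 2 sites each, in K/4 = 4, 3 or 6 blocks.

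**2. The plan's own power.** Section 10 gives d = .51, ICC 0.10, 75 patients per program, 42 programs and alpha 0.05 (two-sided assumed).
- Variance of a program mean, with total variance 1: 0.10 + 0.90/75 = 0.112.
- λ = 42 × 0.51² / (4 × 0.112) = 24.4. Non-central F with 1 and 40 df gives power 0.998.

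The stated floor of .85 is met.

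**3. Type I error of a program-only cross-sectional test when combinations are randomised.** Let s be the share of the between-program variance common to a combination. It is not in the documents, so it is varied. With m sites per combination, the true variance of the treatment contrast exceeds the program-only variance by the factor 1 + (m − 1) × 0.10s/0.112.

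Example, m = 3 and s = 0.5: 1 + 2 × 0.446 = 1.89. The standard error is too small by √1.89 = 1.38, and 1.96/1.38 = 1.42 corresponds to a two-sided error near 16%.

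Simulation used 300,000 null trials per cell, equal combination sizes, a t-test on program means and no covariates:

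| Combinations | s = 0 | s = 25% | s = 50% |
|---|---|---|---|
| 16 of 3 | 5% | 11% | 16% |
| 12 of 4 | 5% | 13% | 21% |
| 24 of 2 | 5% | 8% | 11% |

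The same test when unmodelled blocks explain 30% (assumed) of the variance of combination means:

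| Combinations | s = 25% | s = 50% |
|---|---|---|
| 16 of 3 | 6% | 10% |
| 12 of 4 | 8% | 14% |
| 24 of 2 | 4% | 6% |

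In that second setting, analysing combination means without the block gives about 2.8%, 3.1% and 2.5%. With both terms the error is 5% throughout.

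**4. Coaching power with the combination as unit and a block term.** The 42 programs are spread evenly, so m = 42/K. V = 0.10s + [0.10(1 − s) + 0.012]/m, λ = K × 0.51²/(4V), and df = 3 × (K/4 − 1) = 9, 6 or 15. If blocks remove 30%, V is multiplied by 0.7.

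Example, K = 16 and s = 0.79: V = 0.079 + 0.033/2.625 = 0.0916 and λ = 11.4, which on 1 and 9 df gives power 0.85.

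| Combinations | Power below 0.85 if blocks explain nothing | If blocks remove 30% |
|---|---|---|
| 16 | above about 79% sharing | never |
| 12 | above about 39% sharing | above about 75% sharing |
| 24 | never | never |

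ECHO power cannot be recomputed in this way, because Section 10 calls that effect large without giving a standardised effect size.

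**The case against.** Section 9 may use the word clinic loosely. It allocates all 48 organisations and fixes three jails per arm, and its 12/36 count also fits 12 combinations of one jail and three clinics. The 24/24 figures stand in data-collection paragraphs rather than in an allocation rule, while Sections 6 and 10 agree on 16/32. Section 6 names a cluster randomised block design, and the unnamed program covariates in Section 10 could include the matching factors. Jails and clinics also record different measures (people screened for OUD against people referred from the jail), which makes very high sharing hard to credit.

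Much of this limits the size of the problem; none of it removes the contradiction. The matching lists differ whatever the word clinic means, and Section 9 gives no matching rule for jails. Covariates could absorb some shared variance but do not replace a combination effect.

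Three stronger readings are tempting and not supported:
- A reader might infer that the coaching power claim is false. On the plan's inputs it is met.
- A reader might infer that the trial will certainly declare effects too often. At 25% sharing with the assumed 30% block effect, the error is 6%, 8% or 4%, so inflation can vanish.
- A reader might infer that jails will be separated from their own clinics. Section 9 permits this but does not describe jail-clinic links, so it is a possibility only.

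No figure is given for the intervention-by-time tests. It would depend on how stable both the shared and the program-specific effects are over time, and the documents give neither.

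**Conclusion.** The point holds. Current text leaves the unit of randomisation, the matching list and the jail/clinic split unresolved, and that conclusion needs no assumption. If Section 6 governs, the named models and the power statement omit the randomised unit, and the models also omit the block. Confidence is high on both.

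Confidence in the size is lower. Over 0 to 50% sharing, the program-only cross-sectional test has a Type I error from 5% up to 21% with no block effect. With blocks explaining 30%, it runs from 4% to 14% over 25 to 50% sharing. These ranges rest on one combination per jail, equal combination sizes, no covariate adjustment, and assumed sharing and block strength. Loss of power is secondary: it matters only at high sharing with 16 combinations, or moderate to high sharing with 12, depending on what the blocks explain.

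**What to change.** State one randomised unit, one list of matching factors and one jail/clinic split. Make Section 6 (Study Design and the data paragraphs), Section 9 and the Section 10 power text agree with them.

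If the unit is the jail-clinic combination:
- add a random effect for combination and a term for matched block to the cross-sectional and growth models in Section 10, and to the effectiveness models that build on them;
- base the degrees of freedom for coaching and ECHO on the number of combinations;
- restate coaching and ECHO power for that number, with the block term, as a range over the shared variance, and state the effect size assumed for ECHO.

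If clinics are randomised singly, state how jails are matched and allocated, and how the analysis handles a jail and clinics that fall in different arms.

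The cost is revised wording, one or two model terms and one recalculation. The tests have fewer degrees of freedom, and the single power figure becomes a range that can fall below .85 with 16 or 12 combinations. The correction itself calls for no extra sites.

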10. STATISTICAL CONSIDERATIONS

Sample Size & Power:

Regarding the two intervention factors, coaching and ECHO, in 2x2 factorial design conditions, we will recruit 48 programs, including 16 jails and 32 community-based organizations in the criminal justice system (CJS). This number provides reasonable power to detect the effects of coaching and ECHO on primary outcomes, as previous research indicates estimated effect sizes for the former as medium and the latter as large. A buprenorphine implementation study conducted in 48 treatment agencies in Ohio found that NIATx coaching increased MOUD adoption rates by 24.8% ([name], Quanbeck, et al 2013). More recently, PI [name] found that High vs. Low-Dose coaching provided significantly different results on increases in buprenorphine use among 20 organizations (31.5% vs. 2.5%, $p = .001$, Cohen's $d = .5136$). Other researchers have found large effects for ECHO, including a 10-fold increase in buprenorphine waivered physicians (Komaromy M, Duhigg D, Metcalf A, et al. 2016). Therefore, our power analysis focuses on detecting High- vs. Low-dose coaching effects with an estimated effect size of $d = .51$. Patient outcomes within the same programs may not be independent due to the clustered nature of the data. Based on previous studies, we anticipate the intra-class correlation (ICC) to be around 0.10. Although the number of patients within programs will likely vary over time, our current and previous studies with similar populations and designs suggest that we can anticipate the number of participating programs to be mostly stable during the study period. To increase survey completion, programs will be given a \$1,000 bonus for providing a year of data per site; for government agencies we will provide program materials such as wrist bands, stress balls, or other items to share with participants. This approach is yielding a return rate of 89% in a current study. With 42 programs at the end of the study after 11% attrition and 75 or more patients per program, we will be able to detect coaching effects at a power of .85 or higher in our proposed study with a Type I error rate of 0.05. The corresponding power for ECHO would be greater (.90+) with the same number of programs and patients. Power analysis software developed for clustered data, Optimal Design, was used to calculate power.

Data Analysis Plan:

Initial exploratory analyses of MOUD initiation and use will assess standard summary statistics and examine graphical representations of the data and will compare baseline characteristics among the 48 participating programs in this study, including patient age, ethnicity, nature of SUD, criminal justice status, organizational readiness for change, and MOUD. Chi-square and t-tests will be used to test for statistically significant baseline differences. Descriptive statistics and figures will display the distribution of each analytic variable collected at each time point.

The rates and frequency of MOUD use (buprenorphine, methadone and injectable naltrexone) will be measured repeatedly, and these values will be correlated over time. Instead of assuming independence (i.e., zero correlation) or a compound symmetry covariance structure (i.e., a constant correlation regardless of the proximity of measurement time points), we will allow errors to be auto-correlated or Toeplitz-structured, denoted as AR(p) or TOEP(p), in growth curve models. The best-fitting covariance structure will be determined based on heuristic model comparison criteria such as AIC and BIC.

Intervention and Sustainability:

For MOUD and implementation outcomes at 12 month and at 24 month, mixed-effects models (random effects of programs; fixed effects of treatment condition and time) will be used for data analysis. Mixed-effects models, also known as multilevel or hierarchical linear models, are suitable because MOUD patients are nested within programs. Using a multilevel modeling framework, separate models will be applied for the percentage of patients and clinicians using MOUD and their frequency of use (for patients only). Program covariates as well as variables showing noticeable changes between phases will be included in the models as covariates to properly and efficiently estimate the effects of coaching and ECHO. We will examine the coaching and ECHO effects at each time point using cross-sectional multilevel models and will also implement growth curve models across time that include the coaching (high vs. low) and ECHO (present vs. absent) effects, time (baseline, post intervention, follow-up), and interactions between the intervention and time factors, while controlling for relevant time-varying and time-constant covariates. The rates and frequency of MOUD use (by buprenorphine, methadone and injectable naltrexone) and clinical and implementation outcomes will be measured repeatedly for the same programs, and it is expected that these values will be correlated over time. Therefore, instead of assuming independence (i.e., zero correlation) or a compound symmetry covariance structure (i.e., a constant correlation regardless of the proximity of measurement time points), we will allow errors to be auto-correlated or Toeplitz-structured,⁸² denoted as AR(p) or TOEP(p), in the growth curve models. The best-fitting covariance structure will be determined based on heuristic model comparison criteria such as AIC and BIC.

Mediation analysis:

We will examine the mediating effects of organizational factors on MOUD use through: NIATx Fidelity, ECHO Fidelity, the Organizational Readiness for Implementing Change (ORIC), Program Sustainability Assessment, and the Organizational Climate (Stress) measure. These factors will be analyzed using mixed-effects models. Through a mediation analysis, we can estimate the direct (NIATx and ECHO) and indirect effects (Adoption - # of prescribers) of each implementation arm.

We will test the mediation effect of each potential mediator at each time point as well as across time. The R package 'mediation,' will estimate the causal mediation effects, examine moderated mediation effects, and conduct sensitivity analysis.⁷⁰

Effectiveness analysis:

We will compare MOUD use and retention rates in the 4 different arms using hierarchical linear models, where arm membership is used as the treatment assignment. We will examine the distribution of this outcome measure and will implement an appropriate transformation or nonlinear link function when appropriate (e.g., logistic, Poisson, exponential). Monthly data collection of the Effectiveness as well as Reach (MOUD use) measures, allows for analysis after each stage of NIATx and ECHO.

Table 4: Initiation & Retention

	Data	Source
Initiation	
• # of clients initiated on MOUD• # on MOUD	Organizational Spread Sheet
Retention	
• # of injections• # of weeks on Buprenorphine (30-Day Discontinuation)• # of methadone doses	State Database

Qualitative Analysis:

The qualitative analysis will be conducted by project staff, supervised by the qualitative methodologist, who will ensure that proper and consistent interviewing and analysis techniques are used. Project staff will conduct the interviews, which will be audio recorded and transcribed verbatim. Interviews with leadership personnel will focus on organizational culture, including the organization's approach to making process changes, as well as motivations and expectations for working with justice-involved populations. Interviews with staff will focus on the staff's perspectives on their organizations' experiences with identifying and implementing process changes. Project staff will conduct a directed content analysis of these data. Qualitative data will be summarized and analyzed to detect patterns in individual and clinical approaches to change that have been successful. This description will enhance our understanding of how the NIATx and ECHO models work in criminal justice settings and criminally involved populations, promoting valuable insights that can be applied to future dissemination and implementation of evidence-based practices.

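### If whole jail-clinic combinations are randomised (Section 6), the program-only random effect in Section 10 omits the randomised unit, and the stated 0.05 type I error is not secured

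*Combined protocol and SAP*

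**What the plan says.** **Randomisation.** Under Study Design in Section 6: "Within the matching block of 4 jail-clinic combinations, one jail-clinic combination will be randomized to an arm of the study". Each jail and each clinic within a combination is a separate site: "if a jail has two post incarceration CB treatment providers (or clinics) in the trial, this will be 3 total sites". Blocks are formed on combination-level features: "Matching will be based on; a) number of clinic sites the jail will be including in the study", then county population and current MOUD provision. The expected result is balance, "with an anticipated 4 jails and 8 post-incarceration CB provider sites per arm".

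**Power.** Under Sample Size & Power in Section 10: "we will recruit 48 programs, including 16 jails and 32 community-based organizations". A program is therefore a single site. The calculation is stated as "With 42 programs at the end of the study after 11% attrition and 75 or more patients per program", at a type I error of 0.05.

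**Analysis.** Under Intervention and Sustainability in Section 10: "mixed-effects models (random effects of programs; fixed effects of treatment condition and time) will be used for data analysis". The reason given is that patients are nested in programs. Covariates are left open: "Program covariates as well as variables showing noticeable changes between phases will be included in the models as covariates".

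**Competing text.** Section 9 matches groups of four clinics and randomises one clinic from each group to each arm. It lists 3 jails and 9 community organisations per arm. The administrative data part of Section 6 speaks of 24 jails and 24 providers.

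**The concern.** Under Section 6 a jail and its clinics are allocated together, so the comparison of arms rests on combinations, of which there are about 16, not on 48 independent sites. Section 10 has no combination effect, cluster-robust variance, degrees-of-freedom rule or block term. The AR and Toeplitz structures it names deal with correlation over time within a program, not with correlation between sites that share an allocation.

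If sites in a combination are positively correlated, the standard errors for coaching and ECHO are too small. Positive correlation is plausible, because clinics report people referred to them by the jail, but the documents give no value for it. Omitting the matched block works the other way and makes the test conservative. At stake is error control for both intervention factors on the primary Reach outcome.

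**Working it through.** **Inputs from the documents.** ICC 0.10; 75 patients per program; d = 0.51; 42 programs after attrition; type I error 0.05; 16 jails and 32 clinics. With three sites per combination, 48/3 = 16 combinations and 16/4 = 4 blocks. That gives 4 combinations per arm, i.e. 4 jails and 8 clinics, so Section 6 agrees with the Section 10 counts.

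**Assumed, because the documents are silent.** A two-sided test; the share *s* of between-program variance that is common to a combination (25% / 50%); the part of that share lying between blocks; any jail-clinic difference in outcome.

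**Step 1: the plan's own figure.** With programs as independent clusters, λ = J·d²/[4(ICC + (1 − ICC)/n)] = 42 × 0.2601/[4 × (0.10 + 0.012)] = 24.4. Power is 0.998, so the stated floor of .85 is met on the plan's terms.

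**Step 2: closed form, 16 combinations of 3, no block variance.**
- Variance assumed by the program-only model: 4 × 0.112/48 = 0.00933.
- True variance: 4 × [0.10s/16 + (0.10(1 − s) + 0.012)/48] = 0.01350 at s = 0.25 and 0.01767 at s = 0.50.
- SE ratio: √(0.01350/0.00933) = 1.20 and √(0.01767/0.00933) = 1.38.
- Error: 2[1 − Φ(1.96/ratio)] = 10.3% and 15.4%.

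**Step 3: simulation under no effect.** With equal patients per program, the program random-intercept model is equivalent to least squares on program means (45 df). Each setting used 40,000 trials, except the combination-level covariate row (12,000).

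| Program-only model | s = 25% | s = 50% |
|---|---|---|
| 16×3, no block variance, no gap | 10.7% | 16.5% |
| half the shared variance between blocks | 6.7% | 9.2% |
| three quarters between blocks | 5.0% | 5.2% |
| all of it between blocks | 3.2% | 1.9% |
| block sizes 2, 3, 3, 4; no block variance | 11.2% | 17.4% |
| same sizes, half between blocks | 7.6% | 10.0% |
| 16×3, unmodelled jail-clinic gap 0.3 SD | 8.1% | 12.5% |
| gap 0.5 SD | 4.7% | 8.3% |
| gap 0.5 SD, half between blocks | 2.4% | 3.2% |
| gap 0.5 SD, site type as covariate | 11.0% | 16.6% |
| gap 0.5 SD, site type as covariate, half between blocks | 6.9% | 8.8% |
| covariate explaining half the combination variance | 8.2% | 12.5% |
| 24 combinations of 2, no block variance | 7.5% | 10.6% |
| 12 combinations of 4, no block variance | 13.7% | 21.6% |

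Indexed instead by the within-combination correlation, at −0.25, −0.10, 0, 0.05 and 0.10 the error is 0.9%, 3.0%, 4.9%, 6.2% and 7.1%.

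**Step 4: growth models.** For change from baseline, with an assumed program correlation over time of 0.8, the treatment-by-time test stays at 5.0% if the combination effect is constant. If 25% / 50% of program-by-time variance is combination-by-time, the error is 8.7% / 13.0%, or 6.4% / 7.7% with half of that between blocks.

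**Step 5: candidate remedies.**
- Combination plus block: 4.7–5.3% in every layout, gap and block setting tried.
- Block without combination (s = 50%, half between blocks): 13.2%, worse than the 9.2% of the program-only model.
- Combination without block, same case: 2.4%, valid but conservative.

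**Step 6: if Section 9 governs.** The program is then the right unit. Omitting the block gives 2.8% / 1.2% at a block share of 25% / 50%, so the test is conservative.

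**The case against.** The strongest reply is that the model in Section 10 is wrong only if Section 6 governs. Under Section 9 it has the right unit, so the certain defect is the contradiction between those sections. That is fair, and the finding is conditional for this reason. Section 6 is nevertheless the detailed design text, and its jail and clinic counts are the ones that match the power section.

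Second, the largest figures assume no block variance, although the plan expects blocking to reduce variability and matches on combination-level features. If three quarters of the shared variance lies between blocks, the inflation disappears in the 16×3 layout. A large unmodelled jail-clinic gap would also hide it: at 1 SD the error is 0.4% / 1.3%. The referral link shows that patients move from jail to clinic; it does not prove that MOUD rates are positively correlated. All of this stands, and it rules out quoting one inflation figure.

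It does not rescue the test. Error control should not depend on unknown variance components cancelling. The offset from a jail-clinic gap is lost if site type is among the unnamed program covariates.

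Third, planned power is hardly threatened. That is largely correct, but it concerns power and not type I error.

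**Conclusion.** The concern holds, conditional on Section 6. If combinations are randomised, the stated model leaves out the randomised unit and does not secure the 0.05 type I error for coaching and ECHO. At 25–50% shared variance in the 16×3 layout without a jail-clinic gap, the true error is about 11–17% with no block variance and about 7–9% with half of that variance in blocks. It is at or below 5% when block variance, an unmodelled jail-clinic gap or negative correlation dominates. Neither direction nor size can be fixed from the documents. Confidence is medium: the structural omission is clear, but the shares are assumptions, and the simulations use equal patient numbers and a continuous outcome. The point should be settled before analysis.

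**What to change.** 1. Reconcile Sections 6 and 9 on the randomised unit, and Sections 6, 9 and 10 on the numbers of jails and clinics.
2. If combinations are randomised, add a combination random effect with programs nested in it (and combination-by-time in growth models), the matched block, and site type. Do not add block alone.
3. Base small-sample degrees of freedom on combinations. With 16 combinations in 4 blocks: 16 − 1 − 3 − 2 = 10, or 9 with a coaching-by-ECHO term.
4. For logistic or Poisson models, use an equivalent small-sample correction or a permutation test. Permute coaching within block with the ECHO assignment held fixed (4 arrangements per block, 4⁴ = 256 for 4 blocks), and ECHO likewise with coaching held fixed. With an assumed ECHO effect of 0.8 SD this gave 4.5–4.8% error for coaching. Permuting without regard to ECHO gave 0.0% error and only 27–28% power at d = 0.51.
5. Restate power with the combination as cluster, after 11% attrition.
6. If single clinics are randomised, keep the program random effect and add the matched block.

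**Cost.** Protocol and SAP wording, a few lines of model code and a new power calculation; no new data. Intervals may widen and degrees of freedom fall. With combination plus block, d = 0.51 and no block variance, coaching power at 25 / 50 / 80% shared variance is about 93 / 86 / 77% if two whole combinations are lost (14 × 3 = 42 programs, 8 df). It is about 96 / 92 / 85% if six single sites are lost. With half the shared variance in blocks it is at least 94% in both cases. The stated .85 therefore survives unless most between-program variance is shared within combinations.
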